## SECTION 7. Informed Consent/Parental Permission/Assent Process

Choose all that apply and attach appropriate forms to this application. (Templates available at <http://www.irb.wsu.edu/>) Note: For a list of required elements of informed consent see the definitions at <http://www.hhs.gov/ohrp/humansubjects/guidance/45cfr46.html#46.116>.)

 See WSU BPPM Section 70.44 and <https://policies.wsu.edu/prf/documents/2017/04/70-44-gift-cards-cash-equivalents-purchase-use.pdf/>, <https://policies.wsu.edu/prf/documents/2017/04/45-53-incentive-payments-research-participants.pdf/>, <http://policies.wsu.edu/prf/documents/2017/10/45-53-distribution-log-for-payments-of-cash-gift-cards-and-other-cash-equivalents-and-tangible-property.pdf>, and <http://policies.wsu.edu/prf/documents/2017/10/45-53-record-of-distribution-and-request-for-taxpayer-number-and-certification.pdf>

**DO NOT DELETE OR ALTER ANY PART OF THE APPLICATION**

1.  Adult(s)  Parent(s)  Guardian(s)

 Written	A consent or permission form that contains all of the required elements of informed consent.
 Alteration of Informed Consent process	Requesting IRB approval for waiver of some or all of the elements of informed consent or permission (i.e. medical record review, deception research, or collection of biological specimens). If checked, complete Addendum 4 and submit with the application.
 Waiver of Documentation of Informed Consent	Requesting IRB approval for waiver of the requirement for documentation of informed consent or permission (i.e. telephone survey or mailed survey, internet research, or certain international research). If checked, complete Addendum 5 and submit with the application.
 Waiver of Informed Consent Process	Requesting IRB approval for waiver of the requirement for the informed consent or permission process (i.e. medical record review, deception research, or collection of biological specimens). If checked, complete Addendum 6 and submit with the application.

2.  Children  Vulnerable Population

 Written	An assent or consent form that contains all of the required elements of informed consent.
 Alteration of Informed Consent process	Requesting IRB approval for waiver of some or all of the elements of informed consent (i.e. medical record review, deception research, or collection of biological specimens). If checked, complete Addendum 4 and submit with the application.
 Waiver of Documentation of Informed Consent	Requesting IRB approval for waiver of the requirement for documentation of informed consent (i.e. telephone survey or mailed survey, internet research, or certain international research). If checked, complete Addendum 5 and submit with the application.
 Waiver of Informed Consent Process	Requesting IRB approval for waiver of the requirement for the informed consent process (i.e. medical record review, deception research, or collection of biological specimens). If checked, complete Addendum 6 and submit with the application.

3. What steps have you taken to prevent potential coercion or undue influence in recruiting subjects and obtaining consent or assent?

**Explain in detail:** All personnel involved in recruitment will be briefed to understand consent process, voluntary nature of study, and participant rights to refuse. This is stated in the consent and will be reiterated verbally. Scripted messages will be used to standardize interactions between facility collaborators and participants to protect and preserve rights. Participant identities will be disclosed to clinic medical staff only as needed for mental health safety and evaluation purposes. All other communications regarding recruitment and study activities will be directed towards clinic staff who do not have any investment in the study outcomes.

## SECTION 8. Risk and Benefit Assessment

1. Potential risks to participants: (Check all that apply). *These risks must also match the Risks listed in the Consent/Accent/Permission documents as well as mitigation strategies in Section 8.4 and 8.5.*

- Invasion of privacy to the subject or family
- Breach of confidentiality
- Physical harm or discomfort
- Psychological/emotional discomfort or distress
- Psychological effect that is more than discomfort or distress
- Social stigmatization
- Economic (e.g., employment, insurability)
- Legal
- Any study related activity which subjects might consider sensitive, offensive, threatening, or degrading?
- Withholding standard care and procedures
- Significant time or inconvenience
- Other:

2. Does the study pose risk to individuals other than the participants? no

Explain in detail:

3. Indicate which of the category listed below accurately describes the specific potential risk level based on all items in Section 8, question 1 on the application:

- No more than minimal risk to participants
- More than minimal risk to participants.

 "Minimal risk" means that the probability and magnitude of harm or discomfort anticipated in the research are not greater in and of themselves from those ordinarily encountered in daily life or during the performance of routine physical or psychological examination or tests. 45 CFR 46.102(i).

- Research not otherwise approvable which presents an opportunity to understand, prevent, or alleviate a serious problem affecting the health or welfare of subjects (usually emergency research).

4. How will you minimize these potential risks in order to protect subjects' rights and welfare?

Explain in detail:

Privacy/confidentiality:

Participants will be told that there are potential risks from taking part in this study, such as the loss of confidentiality that comes from giving out personal information. They will be told the research team is minimizing this risk by using a secure web site and not attaching any identifying information like names or social security numbers that will be connected to survey information. Data will be coded and secured. Email communications will be deleted to decrease breaches of privacy and an approved survey program. Qualtrics and OneDrive will be used to maximize security. Zoom technology will be used for videoconferencing due to its enhanced protection features and no participant sessions will be recorded.

Psychological/ emotional discomfort/distress:

Participants will be told on informed consent about potential psychological risk with these statements: "It is possible you will feel stress or psychological discomfort when you are answering personal questions or engaging in any of the non-drug treatment options. You are encouraged to contact any member of the study team if you feel you need additional counseling or other support, and we will refer you to the appropriate services."

Physical harm/discomfort/:

Occasionally, participants may have adverse effects from any one of the chosen non-drug treatment options such as pain, muscle strain, or increased fatigue. These risks will be reduced through the screening histories, physical exam by each treatment provider, and your own communications with providers about your body and preferences. You will not be forced to do anything you are not comfortable doing or believe may cause you harm.

We have chosen experienced providers to provide treatments who have many years of evaluating patients and who will take every precaution to preserve your safety and well-being.

Significant time: Recognizing that this study entails significant time, we will provide each participant with a written schedule and be sure they understand the time commitment prior to consenting. We will allow flexibility in certain aspects of the study when feasible, such as the appointment days and times and provide reminder calls..

5. In the event that any of these potential risks occur, how will it be handled (e.g. compensation, counseling, etc.)? Include supporting materials.

Explain in detail:

Privacy/confidentiality: Known breaches of confidentiality will be reported to participants and researchers will make every attempt to assure future data protections. Conversations will occur in private areas as much as possible. Medical and eligibility screenings will take place in private.

Psychological/ emotional discomfort/distress: As informed in the consent process, if the study staff learns that depression screening or other study data suggests the possibility of severe or

higher depressive symptoms (as defined by the PHQ-9 guidelines) or participants indicate any suicidal, homicidal, or self-harm plan, that information will be reported to the study medical director and primary provider of record. Participants will be encouraged to seek a professional evaluation and be given a number for the suicide hotline. Research personnel and treatment providers will be trained to notify the PI or study physician if any psychological or emotional distress is noted. The primary investigator or licensed co-investigator will be available at all times to provide advice and intervene as necessary. The participating treatment providers will be given directions on how to handle unexpected medical or mental health events.

**Physical harm/discomfort:** Participant comfort will be assessed after each study treatment session and opportunity will be available to minimize any immediate adverse events. All treatment sessions will be delivered by trained and experienced licensed providers and any problems dealt with using usual procedures that are standard for their professions (see letters of commitment in Appendix), such as stopping treatment when necessary and initiating emergent care (calling 911). Providers will be trained to alert PI for adverse events such as physical symptoms of agitation, increased pain, nausea, tremors, etc. A physician and/or licensed healthcare provider with relevant experience with pain populations (RN, MD) will be available at all times via phone during the treatment sessions to trouble-shoot any adverse events or unexpected responses. If deemed necessary, participants will be seen by a licensed healthcare provider for evaluation. Participants are informed during consent process that they or their health insurance will be responsible for costs if any additional medical or psychological services are needed. The study team will assist in connecting them with resources if needed using state sponsored services.

**Significant time:** If unexpected time delays occur due to scheduling conflicts or other unanticipated delays, the PI will express appreciation and offer apologies with an additional \$10 gift card as a thank you for additional time spent.

6. Is it possible that you will discover a subject's previously unknown physical or psychological condition (e.g. disease, depression, suicidal ideation, genetic predisposition, etc.) as a result of your procedures?

YES

NO

If yes, what would they be and how will you handle these situations?

Explain in detail:

It is possible health information will be provided on the surveys that suggests some underlying physical or psychological conditions. These will be reviewed by the PI and followed up with to be sure participants have the resources they need if any concerns arise

7. Describe the expected benefits of this project (*NOTE: compensation is not considered a benefit*):

A. To the individual subjects:

**Explain in detail:** Participants may benefit directly from participation due to the consultation and treatment provided by non-opioid treatments and also receive the satisfaction of contributing to science. It is possible they will receive some relief of pain or emotional distress via the treatment sessions.

B. To society:

**Explain in detail:** The knowledge gained from this study will increase the understanding of whether non-drug pain treatments can assist with opioid dose reduction and symptom management.

8. Explain how, in your assessment, benefits of this study outweigh the risks. (e.g. risk/benefit ratio)

The risks associated with participation in this study are no greater than those ordinarily encountered by adults who seek medical treatment and pain relief of any kind. Because the benefits could be life-changing if they improve outcomes for pain and opioid use, it is our belief that the knowledge gained from this study will outweigh any potential risks.

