**A. Level of Confidentiality**

Delete the highlighted examples in the table below and complete the methods of data for your research to match with the level of confidentiality at each stage of the data. If you have questions, please contact the IRB at [name]. *Guidelines are provided at: <https://orso.wsu.edu/documents/2018/02/guideline-10.pdf/>*

Stages of Data	Level of Confidentiality			
	Anonymous (No identifiers that link the data to a specific subject)	Confidential Unlinked (Collected with identifier, but all identifiers & codes are removed)	Confidential Coded (Linked to a specific subject by a code, not by a direct identifier)	Intentionally Identified: (Linked to a specific subject by personal identifiers)
Collection				Surveys, medication and clinical record data, interview

				recordings
Analysis			Surveys, medication and clinical record data, interview recordings	
Storage			Surveys, medication and clinical record data, interview recordings	
Dissemination	Surveys, medication and clinical record data, interview recordings			

If HIPAA data is being used, increased data protections are required for all systems and IT services that store, process, and/or transmit the data, to include researcher computer endpoints and data collection devices. A signed Business Associates Agreement is required with all third party vendors that store, process, and/or transmit HIPAA protected data.

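### Participants are to be told that surveys carry no identifiers, yet surveys are collected identified, and no one is assigned to read depression scores at a stated time

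*Combined protocol and SAP*

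**What the plan says.** **The assurance.** Section 8, item 4 (Privacy/confidentiality) describes what participants will be told: the team reduces the risk of disclosure by using a secure site and by "not attaching any identifying information like names or social security numbers that will be connected to survey information". The next sentence adds "Data will be coded and secured", but does not present this as something participants hear.

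**The declared status of the surveys.** In the Section 4.A table, the collection row lists "Surveys, medication and clinical record data, interview" recordings under the category defined as "Linked to a specific subject by personal identifiers". The same data types move to the coded category for analysis and storage.

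**The safety report.** Section 8, item 5 reads "As informed in the consent process, if the study staff learns that depression screening or other study data suggests the possibility of severe or" and continues to higher grades of depressive symptoms, defined by the PHQ-9 guidelines, or any plan to harm oneself or others. In that event "that information will be reported to the study medical director and primary provider of record". Section 7, item 3 foresees disclosing identities to clinic medical staff where mental health safety requires it.

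**Review of survey content.** Section 8, item 6 covers survey information that suggests an underlying condition: "These will be reviewed by the PI and followed up with to be sure participants have the resources they need". No time, event or frequency is attached.

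**The schedule.** The data collection plan in Section 2 has the PHQ-8 at Weeks 0, 3 and 6, and the nurse's McCaffery pain assessment at Weeks 0 and 6 only.

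**The concern.** Two separate weaknesses meet at the depression scale.

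The first is accuracy. Under Section 2 (Procedures) no signature is collected, and completing the baseline survey counts as consent. What participants are told about identifiability therefore carries unusual weight. The surveys ask about depression, anxiety and opioid misuse, in patients for whom a dose reduction is being considered, and a report can go to their own primary provider. An inaccurate assurance matters ethically. It may also affect how people answer scales that the plan lists among its primary self-reported outcomes. The documents give no means of judging the size or direction of that effect.

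The second is safety. A report that depends on staff coming to know of a score works only if someone reads the score promptly. The readable text does not say who scores the scale, when, or whether a high score raises a flag. A severe score could wait unread although the plan intends it to be reported.

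**Working it through.** There is no stated figure to reproduce. The check sets the sections side by side and counts the scores concerned.

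**Step 1: the assurance against the table, stage by stage.**

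| Stage | Section 4.A status of surveys | Fits the assurance in Section 8, item 4? |
|---|---|---|
| Collection | Identified (personal identifiers) | No |
| Analysis | Coded | Yes, if the assurance means no direct identifier |
| Storage | Coded | Yes, on the same reading |

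The conflict is at collection. The table has a coded column, and the plan does not use it for surveys at that stage. Section 3, item 4 says the investigator will de-identify the clinic's medication records on receipt. The readable text describes no matching step for surveys.

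**Step 2: the assurance against the safety report.** The report needs a route from a score to a person. Two readings of the assurance are possible:
- No direct identifier on the survey, but a code with a key. The report can be made.
- No link of any kind. The report cannot be made.

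The sentence on coding supports the first reading. The plan is therefore workable, but a participant who hears only the assurance could take it in the second sense.

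**Step 3: who reads the score, and when.** Inputs: 30 participants (Section 2; Section 5, item 1) and three PHQ-8 time points (data collection plan).

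Scores in total, with full retention: 30 x 3 = 90.

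| Week | Scores | Nurse assessment scheduled? | Linked to reading the score? |
|---|---|---|---|
| 0 | 30 | Yes, after the baseline survey is completed | Not stated |
| 3 | 30 | No | Not applicable |
| 6 | 30 | Yes | Not stated |

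The nurse contact is a pain assessment built on pain and function tools (Section 2, item 2). Nothing says that the nurse sees the PHQ-8 result. The review in Section 8, item 6 covers survey content in general but has no timing.

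**Step 4: instrument and threshold.** The schedule names the PHQ-8, while the reporting threshold refers to PHQ-9 guidelines. Whoever checks the scores needs one consistent rule, so the two places must be reconciled.

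**The case against.** The strongest reply is that the plan already holds together. Data are coded, so the key holder can trace a survey without a name on it. Section 7 foresees disclosure for mental health safety, and Section 8, item 5 says participants learn of the report during consent. The investigator reviews survey information. Participants attend weekly sessions, research staff and treatment providers are trained to pass on any distress they notice, and an investigator is available at all times.

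Most of this stands, and it rules out several stronger readings:

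- A reader might infer that the assurance and the safety report are incompatible. They are not, because a code suffices. Nor does the text require a name on the survey.
- A reader might infer that participants are misled overall. The consent form is not among the readable pages, and item 5 says the report is disclosed there. What can be said is that the quoted assurance is inaccurate at collection.
- A reader might infer that all surveys are completed alone online. Electronic delivery through Qualtrics is stated for the baseline survey. The mode at Weeks 3 and 6 is not readable.
- A reader might count 60 scores (Weeks 3 and 6) without a scheduled clinician contact. The nurse assessment at Week 6 rules that out.
- A reader might attach a probability to the gap. With an assumed 2% to 10% of participants scoring severe, the chance of at least one among 30 is 1 - 0.98^30 = 0.455 to 1 - 0.90^30 = 0.958. The documents give no rate, and this is the chance that a severe score occurs, not that it goes unread.

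The reply does not repair the wording at collection or supply a time for reading scores. The weekly sessions are a partial safeguard, since providers can report what they notice, but nothing gives them the scores.

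**Conclusion.** The point holds in two limited parts.

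First, the assurance in Section 8, item 4 contradicts Section 4.A at the collection stage. It must be reconciled with that table, with Section 7, item 3 and with Section 8, item 5. This rests on the text alone.

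Second, the safety report has a passive trigger, and the investigator's review has no stated timing. Of up to 90 depression scores, the 30 at Week 3 fall where no nurse assessment is scheduled. The 30 at Week 0 and the 30 at Week 6 have a nurse pain assessment that is not tied to the score. The counts assume 30 enrolled and full retention. The gap is one of unspecified timing, not of absent review, and how often a severe score would be delayed cannot be estimated from the documents.

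The mismatch between PHQ-8 and PHQ-9 is a smaller inconsistency in the same reporting rule. These changes should be made, but none of the points undermines the pilot's design.

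**What to change.** **Wording.** In Section 8, item 4 and in the consent, state that surveys are identifiable when collected, are coded afterwards with the investigator holding the key, and are re-linked where a safety report is needed. Bring Section 4.A, Section 7, item 3 and Section 8, item 5 into line with that statement.

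**Active check.** Replace the passive trigger in Section 8, item 5 with a defined step: every depression score is checked on receipt at Weeks 0, 3 and 6. Where the survey is electronic, an automatic platform alert carrying the study code can do this. Otherwise a prompt review by the investigator can. A score that meets the study's threshold then follows the existing report path. Give the review in Section 8, item 6 the same timing.

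**Instrument.** Reconcile the PHQ-8 in the data collection plan with the PHQ-9 guidelines cited for the threshold. The threshold and the clinical response remain with the study team.

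**Cost.** Revised wording in a few places, plus a survey setting or a short task per survey. Participants will learn that their answers can be linked back to them, which may make some less candid, and the investigator must handle the alerts.

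### Participants set an opioid goal that may be a dose reduction, but the visible risk wording covers only the questions and the non-drug options and gives no advice to contact the prescriber first

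*Combined protocol and SAP*

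**What the plan says.** Section 2, item 1 (Design) has primary care providers invite patients for whom a lower opioid dose is being considered. Under Section 2, item 2, each participant writes one goal about prescribed opioid use in the baseline survey. The two examples are a lower dose and not going up. The survey comes before the nurse's first assessment. The Data collection plan table lists the medication goal at Weeks 0, 3 and 6.

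Section 8, item 4 describes the risks. On physical harm: "Occasionally, participants may have adverse effects from any one of the chosen non-drug treatment options such as pain, muscle strain, or increased fatigue". On psychological harm, the wording to be given in the consent is that participants may feel "stress or psychological discomfort when you are answering personal questions or engaging in any of the non-drug treatment options".

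Section 8, item 5 describes the response:

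- Symptom alerts: "Providers will be trained to alert PI for adverse events such as physical symptoms of agitation, increased pain, nausea, tremors, etc".
- After sessions: "Participant comfort will be assessed after each study treatment session".
- Clinical cover during sessions: "A physician and/or licensed healthcare provider with relevant experience with pain populations (RN, MD) will be available at all times via phone".
- Follow-up: "If deemed necessary, participants will be seen by a licensed healthcare provider for evaluation".
- Treatment providers also receive "directions on how to handle unexpected medical or mental health events".
- For severe depressive symptoms, or a suicidal, homicidal or self-harm plan, "that information will be reported to the study medical director and primary provider of record".

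Elsewhere in Section 8, opioid reduction and opioid outcomes appear only as benefits (items 7B and 8).

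**The concern.** Goal setting is a study procedure, and it can prompt a participant to take less opioid. That withdrawal symptoms or worse pain can follow is general clinical knowledge; the documents do not state it. A participant who follows the plan as written may adopt a reduction goal before any study clinician has assessed them. The visible text gives them no warning of what taking less may bring and no advice to speak to the prescriber first. Section 8 counts less opioid use as a possible benefit but does not name it as a source of risk, so the visible risk-benefit statement is one-sided on this point. What is at stake is preventable discomfort or an unsupervised dose change, not the validity of an estimate.

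**Working it through.** There is no figure of the plan's to reproduce. The check sets the relevant places side by side.

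1. **Does a study activity bear on opioid dose?** Yes. The goal item does (Section 2, item 2), and it is scheduled three times (Data collection plan).
2. **When is the first goal written?** In the baseline survey, after the consent meeting and before the nurse's pain assessment (Section 2, items 1 and 2). Any warning in time for the goal has to be in the consent discussion, the consent form or the survey itself.
3. **Which sources of harm does item 4 name?** For physical harm, the non-drug options. For psychological harm, the questions and the non-drug options. Opioid change is not among them. The category list in item 1 has no entry for it either, although the tick marks and any free text there cannot be read.
4. **Is there advice to contact the prescriber before a dose change?** None in Section 8, items 4 to 8, and none elsewhere in the supplied text.
5. **Does the alert step ask about opioid change?** Item 5 lists symptoms that go to the principal investigator, whom Section 2, item 1 describes as a nurse certified in pain management. Agitation, nausea, tremor and increased pain could all occur when opioids are reduced, and the list is open-ended. It includes no question about recent opioid change.
6. **What would pick up an event afterwards?**
   - the alert list and the comfort check after each session;
   - phone cover during sessions, and a separate statement in item 5 that the principal investigator or a licensed co-investigator can always be reached;
   - surveys after each modality trial that cover symptoms and medication use (Section 2, item 2), with health information reviewed and followed up by the principal investigator (Section 8, item 6);
   - clinic records of dose, prescription date and dose changes (Section 3, item 4).

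Steps 3 and 4 show a gap before an event. Step 6 shows reasonable cover after one. Step 5 is a small gap between the two.

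**Scale from the schedule, at full enrolment and attendance.** Inputs: 30 participants (Section 5, item 1), 3 goal time points (Data collection plan), 6 sessions each (Section 2, item 2).

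- Goal contacts: 30 × 3 = 90. With the permitted ±10% enrolment (27 to 33): 27 × 3 = 81 to 33 × 3 = 99.
- Sessions at which an alert could be raised: 30 × 6 = 180. With 27 to 33: 27 × 6 = 162 to 33 × 6 = 198.

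These are counts of opportunities. They say nothing about how many participants would reduce their opioids or have symptoms.

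**The case against.** The best case against the point has four parts.

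**The study tapers no one.** Any reduction belongs to usual care under a prescriber who was already considering it, and the goal may simply be to avoid an increase. This stands as far as dosing goes: a reader might infer an unsupervised study taper, and the documents contain none. But the goal item is the study's own procedure, so its foreseeable effects belong in the study's risk wording.

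**The warning may sit in documents that are not supplied.** This also stands. The consent form, scripts, survey items and training content cannot be seen, so the point does not extend to them. Section 8, item 1 requires its risks to match the consent, so if the consent does carry the warning, Section 8 should carry it too.

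**The safeguards are substantial.** They are. A reader might infer that opioid-related symptoms would go unnoticed; the alerts, clinician cover, survey review and chart data make that unlikely. None of them, however, is written to advise the participant before a dose change.

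**Two further claims would go too far.** A reader might take Section 7, item 3, which limits disclosure of identities to clinic medical staff, as blocking referral to the prescriber. That sentence answers a question about coercion in recruitment and consent, and it already permits disclosure for evaluation. A reader might also expect an opioid question at alerts to separate effects of the sessions from effects of reducing opioids. It cannot, because it yields nothing on participants without alerts. The surveys and charts, which cover all participants, suit that purpose better.

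**Conclusion.** The point holds as a modest preventive gap. The visible risk wording omits the effects of taking less opioid and omits advice to contact the prescriber, although the study asks every participant for an opioid goal that may be a reduction. The change is worth making. It does not show that monitoring fails or that the study is unsafe.

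The conclusion rests on three things: the visible text only; the general clinical premise that reducing opioids can cause withdrawal symptoms or worse pain; and the possibility that a written goal prompts a participant to act on it. The documents give no rate for reduction goals, actual reductions or symptoms, so no number of affected participants can be stated. Confidence is medium, mainly because the consent form is not available.

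**What to change.** 1. In Section 8, items 4 and 5, beside the goal item in the survey, and in the consent form if not already there, add wording such as: *Taking less opioid medicine can cause withdrawal symptoms or make pain worse. Please contact the person who prescribes it before changing your dose.*
2. When an alert is raised, have the principal investigator or on-call clinician ask whether opioid use or dose has recently gone down or up. Treat the answer as a safety prompt only, not as an outcome. If contact with the prescriber is needed, make it with the participant's agreement.

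No dosing rule, endpoint or analysis changes. The cost is a few sentences, a slightly less favourable risk statement and one extra question per alert.
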